Diabetes is a very common comorbidity in hospitalized patients. Patients with diabetes are highly likely to be hospitalized, with insulin use increasing this likelihood (1). It is estimated that up to 38% of patients in the hospital have diabetes or hyperglycemia, and likely many more have pre diabetes (2). Diabetes is associated with worse hospital outcomes including increased risk for falls, infections and readmissions. The hospital stay represents an opportunity to intervene and optimize diabetes management. Patients at our hospital also have access to specialized services including endocrinologists and certified diabetes educators. However, diabetes is a complex disease and is common for patients to feel overwhelmed with the burden of therapy. Continuous glucose monitors (GCMs) are commercially FDA approved devices for single-patient use that can measure interstitial glucose every 5 minutes. They vary slightly in the number of wear days, display and need of calibrations. Studies have shown that CGM use improves diabetes control and decrease episodes of hypoglycemia (3-5). One barrier for the effectiveness is uptake, they are not prescribed enough by primary care providers, another significant barrier has been cost. The overall goal of this current study is to assess the feasibility of initiating CGM in patients with diabetes at discharge. This strategy has the potential to overcome delay in accessing the technology and control cost.

One study looked at the feasibility of use in older patients with diabetes and dementia in the outpatient setting. In this study, of 17 people consented and 12 completed the study. Patient and caregivers reported that the device was nonintrusive and responded positively about recommending the device (6). Another study in the outpatient setting found that a total of 22 participants (48.9%) completed the study using the minimum number of 3 FreeStyle Libre sensors with 11 of the participants requiring extra sensors due to a faulty or misplaced sensor (7). One study using a 4 month Telehealth outpatient model utilizing CGM, showed 92% (55/60) completed the 4-month intervention, and 78.2% (43/55) met the criteria of follow-up CGM sensor-wear periods >90 days from baseline. This study showed improved time in range and a decrease in A1C by 1.6% (8).

B Study Objectives

B1 Primary Aim

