To determine the feasibility of initiating a continuous glucose monitoring in patients with diabetes at hospital discharge. We hypothesize that starting and continuing to use a CGM at this critical time is feasible. Feasibility is defined as at least 20% of patients with diabetes referred for diabetes education meet inclusion criteria to participate and 75% agree to

participate. From those who participate, at least 50% continue using the CGM at 3 months.

B2 Secondary Aims

1. To characterize the barriers to continuing CGM use after discharge. We will systematically characterize the reasons for discontinuations (issues with wearing device, use, costs, getting refills, etc.)
2. To assess the effect of CGM initiation at hospital discharge on diabetes outcomes: Time in range, health utilization (clinic visits, ED visits, hospitalization), self-efficacy.

C Study Design

C1 Overview or Design Summary

This study will be an interventional, single-arm, open-label, prospective design.

C2 Subject Selection and Withdrawal

One hundred eligible adult patients will be recruited to the study.

2.a Inclusion Criteria

1. 18 years of age or older
2. Have diabetes (type 1 diabetes mellitus, type 2 diabetes mellitus, cystic fibrosis related diabetes mellitus)
3. Hemoglobin A1c greater than or equal to 8.0% or history of hypoglycemia unawareness
4. Able and willing to sign informed consent form
5. Have a valid telephone number
6. Willing to purchase FreeStyle Libre 2 CGM sensors out of pocket after discharge from hospital

2.b Exclusion Criteria

1. Unable to sign informed consent form
2. Have altered mental status
3. Unable to manage diabetes independently at home
4. Have utilized CGM in the past
5. Pregnancy
6. New steroid-induced hyperglycemia
7. Unwilling to participate in the study
8. Have kidney disease requiring hemodialysis
9. Taking high doses of vitamin C daily (greater than 500 mg every day)

2.c Subject Recruitment Plans and Consent Process

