- 5. Teach participant how to trouble shoot the FreeStyle Libre 2 CGM system
- 6. Provide participant with a handout for FreeStyle Libre 2 CGM system

The study physicians or nurse practitioners will provide the participant with a written prescription for three months of the FreeStyle Libre 2 CGM sensors to be filled by participant at their local pharmacy.

D5 Follow Up Telephone Calls

Within 1-3 Weeks after Discharge:

The study team will contact the participant by telephone to obtain the following information:

- 1. Is the participant still utilizing the FreeStyle Libre 2 CGM? If not, why was it stopped?
- 2. What barriers (such as discomfort, behavior modifications, lifestyle changes, diet changes) did the participant have with the FreeStyle Libre 2 CGM to limit use?
- 3. How satisfied with the FreeStyle Libre 2 CGM is the participant?
- 4. Has the participant been admitted to the hospital or been in the emergency department for a diabetes related problem since discharge?
- 5. Has the participant seen their outpatient diabetes provider since discharge?
- 6. What is the participant's current diabetes treatment regimen?

7. The study team will contact the participant to remind them to fill the prescription for a new FreeStyle Libre 2 CGM sensor with local pharmacy.

One Month after Discharge (+/- 5 days):

The study team will contact the participant by telephone to obtain the following information:

1. Is the participant still utilizing the FreeStyle Libre 2 CGM? If not, why was it stopped?
2. What is the average blood glucose for the past 30 days?
3. What barriers (such as discomfort, behavior modifications, lifestyle changes, diet changes) did the participant have with the FreeStyle Libre 2 CGM to limit use?
4. How satisfied with the FreeStyle Libre 2 CGM is the participant?
5. Has the participant been admitted to the hospital or been in the emergency department for a diabetes related problem since discharge?
6. Has the participant seen their outpatient diabetes provider since discharge?
7. What is the participant's current diabetes treatment regimen?
8. Administer the Diabetes Self-Management Questionnaire

Three Months after Discharge (+/- 5 days):

The study team will contact the participant by telephone to obtain the following information:

1. Is the participant still utilizing the FreeStyle Libre 2 CGM? If not, why was it stopped?
2. What is the average blood glucose for the past 30 days?

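### The 3-month continuation criterion rests on one undefined telephone yes/no, so it can be met when true current use is below 50%

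*Combined protocol and SAP*

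**What the plan says.** B1 Primary Aim defines feasibility by three criteria: at least 20% of referred patients eligible, 75% agreeing to take part, and "From those who participate, at least 50% continue using the CGM at 3 months". Continued use is given no wear rule, sensor count or look-back period, in B1 or elsewhere.

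D5 Follow Up Telephone Calls sets out how the data are obtained: "The study team will contact the participant by telephone to obtain the following information". Item 1 of the three-month list is "Is the participant still utilizing the FreeStyle Libre 2 CGM? If not, why was it stopped". Item 2 is "What is the average blood glucose for the past 30 days". The plan does not say that the average is to come from the device, and does not link it to deciding who is still a user.

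On supply, D4 gives the participant a "written prescription for three months of the FreeStyle Libre 2 CGM sensors to be filled by participant at their local pharmacy". Inclusion criterion 6 requires willingness to pay for sensors personally after discharge. No fill record is collected. B2 lists "Time in range, health utilization (clinic visits, ED visits, hospitalization), self-efficacy" as diabetes outcomes, but neither the D2 schedule nor the call lists contain a step that obtains device data. F2 Statistical Methods gives no rule for the continuation criterion.

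**The concern.** Intermittent use is foreseeable here. Participants pay for sensors and collect them themselves. B2 names cost and refills among the expected reasons for stopping, and the first call includes a reminder to fill the prescription. A participant who wore the discharge sensor and means to buy another could honestly answer yes at three months with nothing on the arm. The problem therefore does not depend on dishonest answers: the question has no agreed meaning for a group that the protocol itself expects to see.

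The criterion is a bare cut on a point estimate. If true current use is somewhat below 50%, a few such answers are enough to carry the observed rate over the line, and the report would then say that continuation was achieved.

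**Working it through.** There is no figure in the plan to reproduce: F1 gives 100 patients without alpha, power or precision.

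**Inputs from the documents.** The threshold is 50% (B1). The denominator is N = 100 (C2, F1), or N = 50 if F1's anticipated 50% agreement is applied to the 100.

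**Assumptions, because the documents give neither.** p is the true share currently using at three months. f is the share of non-users recorded as yes. Every true user is first taken to answer yes.

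**Formulas.** Observed yes rate: q = p + (1 − p)f. Chance of meeting the criterion: P(X ≥ N/2), with X binomial(N, q). The f that brings the expected rate to exactly 50% is (0.50 − p)/(1 − p).

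**Example.** p = 0.40, f = 0.20: q = 0.40 + 0.60 × 0.20 = 0.52, and P(X ≥ 50) at N = 100 is 0.692.

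| True rate p | N | f = 0 | f = 5% | f = 10% | f = 20% |
|---|---|---|---|---|---|
| 0.35 | 100 | 0.001 | 0.011 | 0.053 | 0.382 |
| 0.40 | 100 | 0.027 | 0.095 | 0.241 | 0.692 |
| 0.45 | 100 | 0.183 | 0.363 | 0.579 | 0.904 |
| 0.40 | 50 | 0.098 | 0.195 | 0.334 | 0.665 |
| 0.45 | 50 | 0.284 | 0.429 | 0.584 | 0.841 |

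**Misclassification needed for an expected 50%.**
- p = 0.45: 0.05/0.55 = 9.1% of non-users, or 5 people at N = 100.
- p = 0.40: 0.10/0.60 = 16.7%, or 10 people.
- p = 0.35: 0.15/0.65 = 23.1%, or 15 people.

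**Errors in both directions.** If 5% of true users also answer no, q = 0.95p + (1 − p)f. At N = 100 and p = 0.40, f = 10% gives q = 0.38 + 0.06 = 0.44 and a chance of 0.134; f = 20% gives q = 0.50 and 0.540.

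**Effect of too strict a definition.** If 10% of true users failed a confirmation test and no non-user passed, a true 55% would be observed as 0.55 × 0.90 = 0.495. At N = 100 the chance of meeting the criterion would fall from 0.87 to 0.50. Any confirmation rule has to keep this loss small.

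**The case against.** Telephone self-report is a defensible choice for a small single-arm feasibility study followed up wholly by telephone. That stands as to the mode of follow-up, but it does not supply the missing definition.

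The direction of error is not documented. The script gives room for a no: item 1 asks why use stopped, item 3 asks about barriers, and reasons for stopping are a secondary aim. This stands, so f is an assumption. The 20% column requires 12 of 60 non-users to be recorded as yes at p = 0.40 and N = 100; at 5% the chance is 9.5%. Chance alone passes a true 45% rate 18% of the time. The plan does not say how participants who are not reached will count; counting them as non-users would offset some of the error, and excluding them would add to it.

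A reader might infer several stronger points that the documents do not support:
- **That over-reporting would reverse the feasibility conclusion.** B1 has three criteria, and F1 anticipates 50% agreement against the 75% required. If that expectation holds, feasibility fails on agreement whatever the 3-month answers are.
- **That callers are questioning people they trained.** D4 assigns training to diabetes educators and D5 assigns the calls to the study team; the overlap is not stated.
- **That the plan accepts a yes from someone not wearing a sensor.** It has no coding rule either way.
- **That the cited telehealth study sets a standard.** The background reports that 43 of 55 "met the criteria of follow-up CGM sensor-wear periods >90 days from baseline", but this may describe when the wear period fell rather than a continuation endpoint.

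**Conclusion.** The concern holds in a limited form. The criterion is ascertained by one telephone answer with no definition of use and no confirmation, so it can be met when true current use is below 50%. The exposure is mainly at true rates of about 40% to 49%; near 35% it takes about 23% misclassification to bring the expected rate to the threshold. At N = 100, 10% misclassification raises the chance of meeting the criterion from 3% to 24% at a true 40%, and from 18% to 58% at a true 45%. If 5% of users also say no, the 24% becomes 13%.

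These figures show sensitivity under assumed rates; they do not estimate a bias. They concern one of three criteria and do not show that the overall conclusion would change. The change is worth making because it is cheap and gives the criterion a definite meaning.

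**What to change.** In B1, and in D5 three-month items 1 and 2, count a participant as continuing if both of these hold:
- a sensor is on at the time of the call, or at a call-back within the existing ±5 day window, which allows for a sensor that has failed or just expired;
- the participant reads the 30-day average from the reader or app.

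If a sensor is on but the reading cannot be given for technical reasons, record this as a separate category and not as non-use. Report the plain yes/no rate beside the confirmed rate, and say whether both reach 50%. I would not add a proof-of-purchase condition: someone who bought a single sensor in three months would pass it, and each further condition risks losing true users.

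The cost is one wear question, a definition sentence and a little more call time. Some true users may still be missed, so the confirmed rate may be lower; the paired rates show by how much the two measures differ. The answers are still given by telephone, and the rule assumes that the reader or app displays a 30-day average, which should be checked before it is adopted.

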The study team will identify potential participants from patients referred to the diabetes service or diabetes education service. Once a potential patient has been identified, one of the study team members will review the inclusion/exclusion criteria to determine if the patient is eligible to participate.

D2 Schedule of Measurements

VISIT/PHONE CALL (estimated time window)	WHAT WILL HAPPEN?
Screening Visit (~45 minutes)	Review consent form and obtain consent Complete questionnaire, obtain diabetes history
Day of Discharge (~1 hour)	Complete FreeStyle Libre 2 CGM education Attach FreeStyle Libre 2 CGM sensor to your arm
Within 1-3 weeks from discharge Phone Call (~30 minutes)	Questions regarding use of FreeStyle Libre 2 CGM Current diabetes regimen Adverse Events Reminder to take FreeStyle Libre 2 CGM sensor prescription to pharmacy to be filled
1 & 3 Month Phone Call (~45 minutes) [+/- 5 days]	Questions regarding use of FreeStyle Libre 2 CGM Current diabetes regimen Complete questionnaire Adverse Events
6 Month Phone Call (~15 minutes) [+/- 10 days]	Questions regarding use of FreeStyle Libre 2 CGM Barriers to FreeStyle Libre 2 CGM use

D3 Visit 1a: During Hospital Stay

Study team member will meet with participant, review informed consent form and obtain written consent. Study team member will obtain the following information from patient or medical record after consent is obtained:

1. Most recent A1c

- 2. Height/Weight; calculate body mass index (BMI)
- 3. Year of diagnosis with diabetes
- 4. Type of diabetes
- 5. Has patient been admitted to the hospital or emergency department in the past 3 months for a diabetes related problem
- 6. Home diabetes regimen
- 7. Hospital diabetes regimen
- 8. Hospital discharge treatment regimen
- 9. Participant's reason/goal for using FreeStyle Libre 2 CGM
- 10. Does participant have frequent hypoglycemia or hypoglycemia unawareness
- 11. Complete "Diabetes Self-Management Questionnaire"

D4 Visit 1b: Day of Hospital Discharge:

On the day of participant's discharge from the hospital, one of the diabetes educators will complete the following with the participant:

- 1. Teach participant how to set up the FreeStyle Libre 2 CGM
- 2. Teach participant how to attach the FreeStyle Libre 2 CGM sensor to the upper arm
- 3. Teach participant how to measure blood glucose with FreeStyle Libre 2 CGM reader or personal smart phone
- 4. Assist participant download the free FreeStyle Libre 2 app from the app store on smart phone

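### Low priority: the 6-month call has no adverse-event or utilization question, and the barrier item does not prompt for cost or refills

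*Combined protocol and SAP*

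**What the plan says.** **Safety items.** The D2 schedule lists adverse events for the 1-3 week call and for the 1- and 3-month calls. Its 6-month row has only device use and barriers. The D5 six-month list has two items, the use/stop question and the barrier question. The hospital/ED question and the outpatient-provider question, both asked at the three earlier calls, are gone. E2 commits the team to monitoring for as long as patients take part, and requires events to reach the principal investigator within 24 hours, counted from when the team is told. Section 2.d lists hypoglycemia, hyperglycemia and ketoacidosis among the risks, alongside sensor-site problems.

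**Barrier items.** Secondary aim 1 in B2 is "To characterize the barriers to continuing CGM use after discharge". It continues: "We will systematically characterize the reasons for discontinuations (issues with wearing device, use, costs, getting refills, etc". Inclusion criterion 6 requires that participants be "Willing to purchase FreeStyle Libre 2 CGM sensors out of pocket after discharge from hospital", and the background, discussing limited uptake, says "another significant barrier has been cost". At every call D5 asks two relevant questions. One is "Is the participant still utilizing the FreeStyle Libre 2 CGM? If not, why was it stopped"; the other is "What barriers (such as discomfort, behavior modifications, lifestyle changes, diet changes) did the participant have with the FreeStyle Libre 2 CGM to limit use". Refills otherwise appear only at the 1-3 week call, as a prompt to "remind them to fill the prescription for a new FreeStyle Libre 2 CGM sensor with local pharmacy" (D2: "Reminder to take FreeStyle Libre 2 CGM sensor prescription to pharmacy to be filled"). The discharge prescription described in D4 covers three months of sensors.

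**The concern.** Two gaps in the call content deserve attention.

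First, after the 3-month call no planned question asks a participant about adverse events, hospital or ED use, or clinic visits. An event in that period reaches the team only if the participant volunteers it or the team learns of it some other way. E2's escalation rule cannot help with an event nobody has reported. Secondary aim 2 includes health utilization, so the same gap ends planned utilization data at month 3.

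Second, four kinds of barrier are read out as examples, while two that the aim itself names are left for the participant to raise. If prompted items are mentioned more readily than unprompted ones, cost and refill trouble may look less common than it is, relative to discomfort or diet changes. Someone who keeps using the device despite that trouble is asked only the barrier item. The point is most relevant at 6 months, the only planned contact after the three-month prescription period.

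**Working it through.** The plan states no figure on this point, so the check is a call-by-call comparison followed by simple interval arithmetic.

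**Items planned at each call**

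| Item | 1-3 wk | 1 mo | 3 mo | 6 mo | Count |
|---|---|---|---|---|---|
| Adverse events, D2 | yes | yes | yes | no | 3 of 4 |
| Adverse events, D5 | no | no | no | no | 0 of 4 |
| Hospital/ED question, D5 | yes | yes | yes | no | 3 of 4 |
| Outpatient-provider question, D5 | yes | yes | yes | no | 3 of 4 |
| Open stop-reason question, D5 | yes | yes | yes | yes | 4 of 4 |
| Barrier item, D5 | yes | yes | yes | yes | 4 of 4 |
| Cost or refills among its examples | no | no | no | no | 0 of 4 |
| Refill reminder (not a question) | yes | no | no | no | 1 of 4 |

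The D5 adverse-event row says little about month 6, because D5 omits the item even where D2 schedules it. The evidence on adverse events is the D2 row, where the item is present at three calls and absent at the fourth. For utilization the evidence is D5 itself, which asks at three calls and not at the fourth.

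**Length of the uncovered period.** The windows come from D2 and D5: 3 months +/- 5 days, 6 months +/- 10 days. Assuming 30-day months, the calls fall on days 85-95 and 170-190.

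- Nominal: 180 - 90 = 90 days; share of follow-up to the 6-month call 90/180 = 50%.
- Shortest: 170 - 95 = 75 days; 75/170 = 44%.
- Longest: 190 - 85 = 105 days; 105/190 = 55%.

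With calendar months, three months are 3 x 365/12 = about 91 days, and the range is 91 - 15 = 76 to 91 + 15 = 106 days. The month convention does not matter.

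**Who is affected by the barrier wording.** Participants who have stopped are asked why, in open form, at 4 of 4 calls, so cost or refills can be given as the reason. Participants who continue skip that question and get only the barrier item, whose examples omit both.

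**The case against.** The plan can be defended on several grounds.

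- *Barriers.* In B2, costs and refills appear in the sentence about reasons for discontinuation, and D5 meets that with an open question at every call. The examples in the barrier item are illustrative, and D2 lists barriers at month 6 without restriction. The background remark on cost concerns uptake, not continuing users. Open and prompted questioning each have drawbacks, and prompting can inflate mentions. Most of this stands, and it limits the point to continuing users. What remains is that the item already prompts, and does so unevenly: four examples are offered, and two categories named in the aim are not.
- *Adverse events.* The 6-month call is a short persistence check (about 15 minutes) after the 3-month primary time point. The device is commercially available, and the scheduled questions span the three-month prescription. The stop question and the discomfort example could bring out sensor-site problems, and E2 promises monitoring throughout. This is a plausible rationale, but the protocol does not state it, and neither month-6 item asks about the glycemic risks in 2.d.

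A reader might go further and infer that the study will miss cost as a reason for stopping, that adverse events are never collected because D5 omits them, or that participants are unmonitored after month 3. The documents do not support these readings. The stop question is asked at all four calls, D2 schedules adverse events at three, and E2 leaves room for reports from any source.

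**Conclusion.** Both gaps are real and small. About 90 days (75 to 105), roughly half of follow-up to the 6-month call, have no planned adverse-event or utilization question. The barrier item names cost or refills at 0 of 4 calls, which mainly affects continuing users. The absence of an adverse-event item from D5 at the three earlier calls is an editorial mismatch with D2.

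It would be wrong to conclude that the feasibility result is at risk. The B1 criteria, including use at 3 months, do not depend on any of these items. The number of events or barriers that would go unreported cannot be estimated from the documents, and under-reporting of cost among continuing users is a reasonable expectation, not a demonstrated effect. The intervals assume 30-day months and calls made within their windows. The conclusion also assumes that the call forms follow D2 and D5; a form outside these documents could already contain the prompts.

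**What to change.** 1. **Six-month call, in both D2 and D5:** add a question on adverse events since the last call, and add the existing hospital/ED question. That question currently looks back to discharge, so record event dates or ask since the last call to avoid counting earlier events twice.
2. **Earlier calls (editorial):** carry the D2 adverse-event item into the 1-3 week, 1-month and 3-month D5 lists so that the two sections agree.
3. **Barrier item, all four calls:** keep the present examples and add cost, getting refills, difficulty using the device, and 'other'. Keep the stop question open, then code each answer to the same list so that those who stop and those who continue can be tabulated together.

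The cost is a form edit and slightly longer calls, most noticeable at the 15-minute 6-month call, with no new visits or staff. Month-6 answers would rest on about 90 days of recall. Mentions of cost and refills may rise because they are prompted, so reports should say which barriers were prompted and which were volunteered.

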3. What barriers (such as discomfort, behavior modifications, lifestyle changes, diet changes) did the participant have with the FreeStyle Libre 2 CGM to limit use?
4. How satisfied with the FreeStyle Libre 2 CGM is the participant?
5. Has the participant been admitted to the hospital or been in the emergency department for a diabetes related problem since discharge?
6. Has the participant seen their outpatient diabetes provider since discharge?
7. What is the participant's current diabetes treatment regimen?
8. Administer the Diabetes Self-Management Questionnaire

Six Months after Discharge (+/- 10 days):

The study team will contact the participant by telephone to obtain the following information:

1. Is the participant still utilizing the FreeStyle Libre 2 CGM? If not, why was it stopped?

2. What barriers (such as discomfort, behavior modifications, lifestyle changes, diet changes) did the participant have with the FreeStyle Libre 2 CGM to limit use?

E Safety Monitoring

E1 Safety and Compliance Monitoring

The study team will meet every other week to review the status of the study, progress of recruitment, and adverse events. The study team will communicate directly with one another in between scheduled study team meetings if an unexpected adverse event occurs.

E2 Medical Monitoring

The study team will monitor patients throughout their participation in the study. Any adverse event or unexpected adverse event will be brought to the principal investigator within 24 hours of study team notification of event.

F Statistical Plan

F1 Sample Size Determination and Power

One hundred patients will be recruited for the study with the anticipation that 50% will agree to participate in the study.

F2 Statistical Methods

Statistical methods will include descriptive statistics (means, SD, median, IQR) and pre-test/post-test ANOVA for the questionnaire.

G References

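### The barrier question at all four follow-up calls gives no access examples, although secondary aim 1 names costs and refills, and no call records prescription status

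*Combined protocol and SAP*

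**What the plan says.** B2, secondary aim 1, concerns barriers to continued CGM use after discharge and states: "We will systematically characterize the reasons for discontinuations (issues with wearing device, use, costs, getting refills, etc". The Background had already raised access: "One barrier for the effectiveness is uptake, they are not prescribed enough by primary care providers, another significant barrier has been cost". Inclusion criterion 6 (2.a) requires willingness to pay for sensors personally after discharge.

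D4 gives each participant a "written prescription for three months of the FreeStyle Libre 2 CGM sensors to be filled by participant at their local pharmacy". D5 then schedules calls at 1–3 weeks, 1 month, 3 months and 6 months. Each call contains two relevant items:

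- a status item with an open follow-up: "Is the participant still utilizing the FreeStyle Libre 2 CGM? If not, why was it stopped";
- the barrier item: "What barriers (such as discomfort, behavior modifications, lifestyle changes, diet changes) did the participant have with the FreeStyle Libre 2 CGM to limit use".

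The prescription comes up once in the call lists, at 1–3 weeks, when the team is to "remind them to fill the prescription for a new FreeStyle Libre 2 CGM sensor with local pharmacy". In D2, the 6-month call has two contents: questions about use, and "Barriers to FreeStyle Libre 2 CGM use". The plan does not say who, if anyone, renews the prescription after the first three months. F2 gives no categories or coding for stop reasons.

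**The concern.** The aim and the instrument do not match. Two of the four reasons that B2 names are access reasons (cost and refills). The examples in the barrier item all concern tolerability or changes in habits. If interviewers use the examples as cues, some barriers are prompted and the access barriers must be volunteered. Prompted reasons tend to be reported more readily, so a tally of barriers would lean away from cost and supply. In a study whose participants buy their own sensors, those are the reasons most worth counting accurately.

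The second part concerns late stopping. Use is followed for three months beyond the period that the study prescription covers. A participant who says at 6 months that the sensors ran out might have had no valid prescription, been unable to afford more, or chosen not to continue. These call for different remedies, and no listed item separates them.

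**Working it through.** No sample-size or power arithmetic applies. The check compares the aim with the call lists item by item.

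**Aim against prompt.** B2 names four reasons: wearing the device, using it, costs and refills. The barrier item gives four examples: discomfort, and changes in behavior, lifestyle and diet. Of the two access reasons in B2, 0 appear among the examples.

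**The four calls in D5.**

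| Call | Open stop-reason item | Barrier examples include cost or refills | Asks about outpatient diabetes provider visit | Records prescription status |
|---|---|---|---|---|
| 1–3 weeks | yes | no | yes | no (reminder only) |
| 1 month | yes | no | yes | no |
| 3 months | yes | no | yes | no |
| 6 months | yes | no | no | no |

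The barrier examples omit both access reasons at 4 of 4 calls, and prescription status is recorded at 0 of 4. The 1–3 week entry gives the participant information and does not collect an answer. The provider-visit item is the nearest proxy for access to a prescriber, and it is absent from the 6-month call.

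**Prescription against follow-up.** The study prescription covers 3 months (D4), and the last call is headed "Six Months after Discharge (+/- 10 days". The difference is 6 − 3 = 3 months of follow-up beyond the prescription. A sensor is also attached at discharge. The documents do not give its wear time, so no day count is attempted.

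**Which item reaches whom.**

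1. *Stopped because of cost or refills.* The open stop-reason item can capture this if the participant says so. The barrier item can too, without a cue.
2. *Still using, but less often because of cost.* The follow-up on stopping does not apply, so the barrier item is the only listed route, and its examples point elsewhere.
3. *Stopped after month 3 with an ambiguous answer about supply.* Both items may record the answer, but nothing listed separates a lapsed prescription from cost or from choice.

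The gap is therefore narrow. It lies in cases 2 and 3, and in the uneven prompting that affects all three.

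**The case against.** The strongest reply is that aim 1 is about reasons for stopping, and every call already asks for those in an open question. The barrier item is also open, since its examples are offered as illustrations only. B2 itself supplies a natural coding frame. D5 lists information to obtain by telephone and is not shown to be a verbatim script, and the call form is not in the documents. An interviewer who knows the aim may well probe for cost.

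Much of this stands. A reader might infer that the calls collect nothing about cost or refills. That is not supported, because the stop-reason item can collect both from anyone who stopped. A reader might also infer that participants are without sensors from month 3 to month 6, or that the plan hands renewal to outside prescribers. The documents say neither; they are silent on renewal. Nor do they show that prescription status is lost for good if it is not asked, since nothing bars a follow-up question.

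The reply does not dispose of the point. Aim 1 opens with barriers to continued use, so the barrier item is squarely relevant to it, and it is the only listed item that reaches continuing users who limit use because of cost. Possible probing by an alert interviewer is less than the systematic characterization that B2 promises. A coding frame cannot sort an answer when the distinguishing question was not asked.

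**Conclusion.** The point holds as a mismatch between secondary aim 1 and the call items. The two access reasons that the aim names are missing from the barrier examples at all four calls, and no item records prescription status although three of the six months followed lie beyond the study prescription.

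The effect is limited to a descriptive secondary aim. A reader might carry the concern over to the feasibility criterion of at least 50% continuing at 3 months. That criterion depends on whether the device is still used, not on why it was stopped, and it is assessed at about the time the study prescription ends, so it is not affected.

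The likely direction is under-reporting of access barriers relative to the prompted ones. This assumes that the listed examples shape what is asked. The documents give no rate of missed or ambiguous answers, so no bias can be estimated. The point is worth considering because the remedy is small; it is not a serious flaw.

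**What to change.** 1. At all four D5 calls, add cost, getting refills and obtaining a prescription to the barrier examples.
2. At the 3- and 6-month calls, add one yes/no item: does the participant currently have a sensor prescription? Who wrote it need not be asked, as that goes beyond the aim.
3. State that reasons will be coded by the B2 categories, with a code for a prescription that ended or was not renewed, separate from cost and from choice.

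The cost is a few words in one item, one short question at two existing calls and one reason code. Calls become slightly longer, which matters most at 6 months, where D2 allows about 15 minutes.
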